The participants that are assigned to Group 2 will have one additional assessment session at baseline. In order to help those in Group 2 who will not be receiving therapy for the first 8 weeks, individuals in this group will be taught safety planning, given information on local resources to help victims of violence, and will be instructed in stress and anger management strategies. Following this 8 week waiting period, they will receive 8 weeks of couple therapy unless they choose not to. All the physiological and behavioral data collection will be repeated once Group 2 starts therapy.

If a couple discontinues after the baseline and before the end of the study (EOS), the EOS assessments should be obtained.

For couples in Group 1, involvement in the study will last throughout a period of five months with approximately 14 hours of active participation. For couples in Group 2, involvement in the study will last throughout a period of seven months with approximately 16 hours of active participation.

Couple Therapy

Each couple will receive couples therapy for 8 weekly sessions. Each therapy session will last approximately an hour. The therapy sessions will take place in UH Mood Disorders Program, room #12-126, on the 12th floor of the W.O. Walker Center. An attachment and affect regulation based therapy approach will be used in couple therapy.

Principal Investigator: [name]

Protocol Summary for IRB: Feasibility Study of Couple Therapy Treatment for Situational Couple Violence (IRB# 09-13-27)

The participants will receive standard couples therapy that they would have access to outside of the study. The therapy itself is not experimental, but rather it is the data collection, physical measures, and timing which are the experimental portions of the study.

All therapies will be conducted by the PI, [name]. [name] is a Licensed Marriage and Family Therapist and AAMFT (American Association of Marriage and Family Therapy) approved clinical supervisor.

Hypotheses

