The site will be at the Mood Disorders Program in the Department of Psychiatry at University Hospitals. The PI's office will be used as the private area to conduct the couple therapy and to collect physiological data, located in room #12-126 on the 12th floor of the W.O. Walker Center ([name]). It is a large, comfortable room equipped with task chairs, and will be suitable for couple therapy. The Mood Disorders Program also has a waiting area and a receptionist to guide participants through to the therapy room, along with security. For safety measures, the PI's office is equipped with a panic button in case of emergency, and doors in the clinical area are locked with UH access only. The Dahms Clinical Research Unit (DCRU) may be used for physiological data collection.

Obtaining Informed Consent

If potential participants are willing to participate, they will be asked to sign paper copies of the consent form at the initial clinical interview. Informed consent will take place in the PI's office at the Mood Disorders Program. The consent form for participation in this project will include detailed information on the project, study procedures, risks, benefits, alternatives to participation, financial information, confidentiality information, and privacy information. The consent form will also explain how anonymity will be maintained for the questionnaires. Information about

Principal Investigator: [name]

Protocol Summary for IRB: Feasibility Study of Couple Therapy Treatment for Situational Couple Violence (IRB# 09-13-27)

anonymity will also be conveyed verbally, and questions about the anonymity procedures and confidentiality will be answered.

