Digital Data Collection of Patient Assessments: At the beginning of the study, the data management team (DMSAU) will obtain an email address for each research participant enrolled into the study. Throughout the study, this email address will be used to send a link to access the participants-rated survey. This email address will allow the participants to access the participants-rated survey from within the REDCAP server. Through this email address, the participants will be emailed a link to access self-report study assessments. This link will be created through the REDCap “management participant list” tool. This link does not carry any PHI or de-identified data. This link does not expose any information about the participants’ identity or other information. All participants’ responses will be recorded in a secured environment within the REDCAP server. As an additional security measure, the link will expire after the participants completes the participants-rated survey.

If any technical problems emerge that prevent the digital collection of data (accessing the REDCAP server, connectivity, computer technical issue, etc.), the participants can still complete

[figure not shown]
Principal Investigator: [name]

Protocol Summary for IRB: Feasibility Study of Couple Therapy Treatment for Situational Couple Violence (IRB# 09-13-27)

the paper version of the participant-rated survey. While participants will be encouraged to enter their responses digitally, they will continue to have the option of responding on paper if they so choose.

Participants will receive via email a 128-bit hash value (e.g. 3425eee5999025d4847fd3ca1b2a362c) that will uniquely identify them as the appropriate subject, essentially serving as a username and password in one. Participants will click on the link to go to the Self Report Survey in RedCap. All transmissions between the client and RedCap will take place over a 128 encrypted line. Answers will be stored in a MySQL database that is housed in the same HIPAA class data center as the above mentioned Oracle server. The Self Report Survey can still be completed on paper if that is the participant's preference or there are technological difficulties. In that instance, the data will be entered by study staff and will be double checked by second study staff.

Fig 1. Project Flow Chart

Principal Investigator: [name]

Protocol Summary for IRB: Feasibility Study of Couple Therapy Treatment for Situational Couple Violence (IRB# 09-13-27)

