The therapy that participants are receiving is not experimental, rather the data collection procedures comprise the research. After 8 weeks of sessions, if participants request additional therapy, the PI will continue to be their therapist until their issue is resolved or they secure another therapist. The PI will also provide referral information in case participants would like to continue with another therapist.

Data and Safety Monitoring

Data Monitoring. The proposed research will include data from approximately 8 couples. The final dataset will include self-reported demographic and behavioral data, along with cortisol levels and heart rate information. All identifiers will be removed from the final dataset prior to release for sharing.

Data will be reviewed after every assessment session. The PI will analyze the data from the first cohort before proceeding with the next to determine if the research should proceed as planned, if PI needs to modify the protocol or discontinue the research (e.g., if Group 2 is doing better than Group 1).

Safety Monitoring. The PI will be responsible for monitoring the safety of the participants. In this study, the welfare of the participants will be of primary concern during treatment. There are a number of interventions cited in the literature for clinicians concerned about violence occurring between partners in between therapy sessions. Several prevention strategies and safety interventions from the literature will be used to prevent and deal with situations that may arise. These strategies and interventions are described in the attached Safety Chart.

Careful assessment will be conducted to understand the dynamics of situational couple violence and potential safety issues that couples are experiencing. The PI will ask questions about whether participants feel they are in danger. If participants are afraid that their partner will retaliate after disclosing sensitive information, these couples will be excluded from the study. Withdrawal from the study will be honored without any coercion.

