Participation in the study is confidential. Only the PI will know the participants' identity. Data will be de-identified. Traditionally used identifying information about participants, such as name, address, telephone number, or social security number, will not be put into either the public or controlled access databases for this project. Participants will have individual personalized login numbers to ensure that assessments at each data collection time connect to the correct participant. Participants will be contacted via email and telephone to remind them of the 3-month follow up assessment. None of the data will be entered into the participants' medical records and no study information will be shared with participants' physicians.

Confidentiality of the data will be maintained within legal limits. Access to participants' records will be limited to the PI. However, the study records must be available for review. The institutional Review Board (IRB) at University Hospitals of Cleveland, and other regulatory agencies may need to review study records.

The PI will receive a Certificate of Confidentiality from the government. This certificate protects against the involuntary release of information about participants collected during the course of this research. Since IRB approval is required to apply for a Certificate of Confidentiality, the PI will apply for the Certificate of Confidentiality after IRB approval is obtained. Nobody will be enrolled in the study before Certificate of Confidentiality is obtained.

The PI has been trained and certified in human subjects research. Information will be disclosed only with the participant's permission or as required by U.S. or Ohio law. Research personnel involved in this study cannot be forced to disclose any information collected in this study in legal proceedings. However, the PI is not prevented from taking the necessary steps, including reporting to authorities, to prevent serious harm to the subject or others, specifically children. In

Principal Investigator: [name]

Protocol Summary for IRB: Feasibility Study of Couple Therapy Treatment for Situational Couple Violence (IRB# 09-13-27)

this case, an appropriate Department of Children Services in the participant's community will be notified if anyone on the research team suspects a child is experiencing abuse.

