All data and participant contact information will be destroyed at the end of the study period, following publication. If any results of the research are published, no information that could identify the participants will be released.

Data/Sample Security

Data collection and data security will be performed using RedCap. Paper versions for the technical problems will be entered to the redcap system as soon as technical problems were solved. These paper versions will be de-identified and will not include any identifying information. Data collected via RedCap will be password-protected. Participant assessment data will be confidentially downloaded into the CWRU secure computer server. Staff at the Office of Information and Technology at UH and CWRU will ensure downloaded data continues to remain secure, and they will create computer password links so that only the PI can have access to participant data. De-identified data located on the secure UH computer server will be translated into a readable Excel database at the completion of all study assessments. The data will be stored on the Case Western Reserve University network. Data transfers between computers will be protected by SSL encryption. If researchers need to transfer data outside of the network, an ironpad will be used to ensure security of the data.

The status of all participant data will be monitored by the PI on a weekly basis (e.g., assessments completed, drop outs). The data downloaded to Excel will be kept in a password protected program folder on a password protected local hard drive that will be physically located in a locked environment. Although the computer is a part of Case/UHCMC network, the database will not be accessible via the Case/UHCMC network. Only the PI will have the access to the data.

We recognize the sensitive nature of our research and the need to maintain strict confidentiality. We will take the following necessary steps to do so:

1. No record of participation in the study will be entered into the medical records of the participant.
2. We will implement the following schema for managing the linking of the data:
 - a) Prior to participant enrollment, we will generate sets of unique barcode labels, referred to as the ID.
 - b) Informed consent will be obtained and the participant will be enrolled in the study.

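### Questionnaires are described as anonymous, but the answers are individually linked and the only person given identity and data access is the therapist of every couple

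*Combined protocol and SAP*

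**What the plan says.** Obtaining Informed Consent: "The consent form will also explain how anonymity will be maintained for the questionnaires". The next sentence adds that anonymity will also be explained verbally and questions about it answered.

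The sections on data handling describe something else:

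- Data Sample Confidentiality: "Participants will have individual personalized login numbers to ensure that assessments at each data collection time connect to the correct participant". The same section says "Only the PI will know the participants' identity" and "Access to participants' records will be limited to the PI", with the ethics board and regulators as possible reviewers.
- Data/Sample Security: a key joining study ID to personal details is kept in a separate protected database. On access: "Only the PI will have the access to the data".
- Digital Data Collection of Patient Assessments: each participant is emailed a hash value that serves as a personal credential, and "the data management team (DMSAU) will obtain an email address for each research participant enrolled into the study". Where a paper form is used, one member of study staff enters it and another checks it.
- Couple Therapy: "All therapies will be conducted by the PI".
- Data and Safety Monitoring: "Data will be reviewed after every assessment session". The principal investigator is then to analyse the first cohort before going on to the next.

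Under Purpose, Aim 1 takes the presence and intensity of violence from self-report and partner-report questionnaires.

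**The concern.** There are two issues, and they carry different weight.

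The first is a matter of fact. Data that carry a personal identifier, are joined across visits and can be traced through a retained key are coded, not anonymous. A participant told that the questionnaires are anonymous would not expect their own therapist to be the one person able to put a name to the answers. In a study of partner violence, that is something people need to know before they disclose.

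The second is a possible bias. Cortisol and heart rate variability do not measure violence, so the evidence on violence rests on what partners choose to report. After therapy, a couple's answers are accessible to the person who treated them, about one week after a final session devoted to consolidating change. At the end of the wait, Group 2's answers are accessible to someone who has not yet treated them. If reporting shifts with that relationship, part of any apparent fall in violence could be a change in reporting. The plan describes no independent assessor and no barrier between the therapist's role and the outcome answers.

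**Working it through.** The plan gives no figure on this point, so the main check is to set its statements side by side.

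1. **Are the answers anonymous?** Digital Data Collection gives each person a unique credential, Data Sample Confidentiality ties every assessment to the correct person, and Data/Sample Security keeps a linking key. Each of these is incompatible with anonymity. Data Sample Confidentiality itself speaks of confidential and de-identified data, so the plan mixes two terms.
2. **Who can identify them?** Data Sample Confidentiality reserves knowledge of identity, and access to records, to the principal investigator. Data/Sample Security reserves data access to the same person. The holder of the linking key is not named.
3. **Who delivers therapy?** The same person, for all couples.
4. **Does that person see answers during the study?** At screening, yes: under Recruitment the investigator decides eligibility from the prescreening answers, and Screening Measures lists the CTS2 both as a screening tool and as a measure repeated through the study. At the first-cohort analysis, yes. For the review after each assessment session, the sentence names neither reviewer nor content.
5. **Is sole access consistent within the plan?** No. The data management team holds participants' email addresses and staff handle paper forms. The readable Excel file is produced only once all assessments are complete, which is hard to square with review after each session.
6. **What shields the answers?** Behavioral Measures puts partners in separate rooms. That protects answers from the partner, not from the therapist.

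**Illustration of sensitivity.** The documents give no under-reporting rate, so the shifts below are assumptions. There is no true effect, alpha is 0.05 two-sided (the plan states none), and only treated participants shift their reports by b standard deviations. For a two-group t-test with n per group, the statistic is noncentral t with df = 2n − 2 and noncentrality b√(n/2). For a pre-post t-test in n participants, df = n − 1 and noncentrality is b√n, with b in SDs of the change score.

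| Assumed shift b | Two groups, 8 individuals each (df 14, noncentrality 2b) | Two groups, 4 couples each (df 6, noncentrality 1.41b) | Pre-post, 8 individuals (df 7, noncentrality 2.83b) |
|---|---|---|---|
| 0 | 5.0% | 5.0% | 5.0% |
| 0.2 | 6.6% | 5.7% | 7.8% |
| 0.5 | 15.4% | 9.2% | 23.2% |
| 0.8 | 32.0% | 16.0% | 49.6% |

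The columns of 8 treat partners as independent, which they are not.

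Aim 2 names chi-square tests. For an uncorrected chi-square with 8 individuals per group and the same true proportion with any violence in both groups, the false-positive rate by exact enumeration, when 0, 10, 25 or 50% of violent treated participants deny it, is:

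- true proportion 60%: 7.1, 8.2, 12.9 and 28.9%
- true proportion 80%: 2.7, 5.1, 14.4 and 44.7%

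These figures show how sensitive such tests would be to a reporting shift. They do not show that one will occur.

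**The case against.** The case on the other side is substantial.

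- **The consent process already covers reporting limits.** Obtaining Informed Consent says the limits due to mandatory reporting will be discussed in person and on the form. This stands: a reader might infer that participants are misled about mandatory reporting, and the text does not support that. What stays open is whether questionnaire answers count, since the child-abuse trigger is worded around what emerges in sessions. The consent form itself is not in the supplied text.
- **Session-by-session reading by the therapist is not stated.** It is tempting to infer from the sole-access statements, but the review sentence names no one, and the weekly monitoring in Data/Sample Security gives completion and dropout as its examples. This stands.
- **The pressure need not fall on treated couples alone.** Waiting couples were screened by the same investigator, expect to be treated by that person, and are later treated and reassessed. Trust in a therapist could also increase disclosure. This stands; only a difference in degree can be argued, and under-reporting is an inference.
- **Partners report separately on each other.** Hiding violence at couple level would usually need both partners to under-report. This is a real safeguard, but both partners have the same therapist.
- **Reports crossing into joint sessions.** A reader might infer that the therapist will carry one partner's private answers into therapy. No passage says so.
- **The size.** A reader might note that one couple in four is 25 percentage points of a violence-free share. The protocol defines no such endpoint for this study, and the figure reflects only the group size, so it does not measure this problem.
- **Limits of any remedy.** Safety items in this study are largely violence items, and the therapist asks about safety face to face after sessions and calls between them. This stands: restricting access reduces the bias but cannot remove it.

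None of this makes the anonymity statement correct or supplies a barrier between therapist and outcome data.

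**Conclusion.** The anonymity statement is inaccurate on the plan's own terms. The answers are coded and linked, and the only person given identity and data access treats every couple. This part needs no assumption.

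The consequence for the results is a plausible risk, not a demonstrated bias. It rests on the inference that people report violence differently to a therapist who has treated them than to one who has not yet done so. The likelier direction favours therapy, but the documents establish neither direction nor size. The tabulated false-positive rates hold only under their assumed shifts, alpha and units of analysis. With eight couples and violence measured only by questionnaire, the study has little means of separating a reporting shift from a treatment effect, so the point is worth settling before enrolment.

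**What to change.** 1. **Consent form and verbal explanation.** Replace the reference to anonymity with a statement that answers are coded and confidential. Say who can read identified answers, and whether the stated reporting limits also apply to questionnaire answers.
2. **Access.** Set REDCap rights so that the existing data management team holds the outcome scale answers until a couple's follow-up is complete. Until then the treating investigator receives only a set of safety items, listed in advance by the sponsor, as alerts. Leave eligibility screening and all safety checks under Safety Information and Data and Safety Monitoring unchanged.
3. **Reconcile the text.** Bring the access and review statements in Digital Data Collection, Data and Safety Monitoring, Data Sample Confidentiality and Data/Sample Security into line. Name who does the review after each assessment session, and state that the first-cohort analysis uses coded data. With four couples per group the therapist may still recognise a couple from coded records, so group summaries prepared by the data team would be safer.
4. **Limitation.** State the remaining therapist-related reporting bias in the analysis plan and in any report.

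Cost: revised consent wording, an amendment to four sections and a change of user rights. The plan describes the data team only as obtaining email addresses used to send survey links, so its capacity to hold the answers should be confirmed. The therapist will see fewer scale scores during treatment, and some bias remains because safety-related violence items stay visible.

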Attachment positions will become flexible and attachment signals and emotions become clear.

Interventions & Mechanisms:

Enactments: In this stage, the therapist focuses on the partners' attachment needs, and helping them to express and own those needs and their corresponding emotions. The therapist directs one partner to the other partner in a particular way to enact the present interactional position, encourage the new emotional experience to the other, and enact new behaviors. The therapist supports each stated need and attempts to directly choreograph specific change events. The main function of restructuring is to alter the crystallized present position, challenge old patterns of relating, and heighten new or rarely occurring responses.

The therapist monitors the acceptance by others in the room of the person who is expressing his/her new or vulnerable emotional experiences and trying to engage in new interactional patterns. The therapist facilitates everyone's hearing of, processing of, and response to these new experiences. De-escalate the old, destructive interactional cycles and restructure a new and intimate interaction.

End State: The more critical partner is fully softened and acknowledges and shares their own attachment desires and vulnerable feelings. Contact between the partners becomes intense and authentic.

Week 7: Emphasizing Creative Problem Solving

Goals:

The primary goal of this step is to highlight the emergence of new solutions to relationship problems. By this time, a new way of interacting with one another based has been developed on reconnecting events during previous sessions. With this session, the therapist becomes less directive and is a guide to keep interactions on the new level of experiencing one another.

Principal Investigator: [name]

Protocol Summary for IRB: Feasibility Study of Couple Therapy Treatment for Situational Couple Violence (IRB# 09-13-27)

Interventions & Mechanisms:

Encouragement and support. The therapist provides encouragement and support when highlighting the changes that have occurred. The therapist validates each person's movement toward change with specifics regarding what they have changed and what they should continue to strive to change. The therapist particularly supports individuals when they proactively own their part in the interactional cycle by helping their partner to be open and responsive to these new actions. In addition, continued observation of new attachment experiences and questioning about the feelings that are evoked by the new interactions is required. The therapist invites the more hesitant partner to respond or the more vocal partner to be open to other partner's perceptions.

Redirection. At this point, the therapist teaches the partners to begin interrupting their own negative interactional cycles as well as practicing re-attachment strategies and self-softening/soothing techniques. The therapist requests that everyone begin doing this independently so that by practicing new interactions, they become natural.

End State:

Both partners feel able to carry out new tasks in their interactions with one another. They feel connected to one another in new ways. An atmosphere of trust and safety becomes evident as vulnerable feelings are exposed more readily and problem-solving becomes easier because conflict is at the level of differences in opinion rather than insecure attachment interactions.

Week 8: Termination/Consolidation

Goals:

The goal of termination is to consolidate changes that have been made and look toward the future. All participants will be able to reflect on the changes they have witnessed and made as well as the feelings these changes have evoked. A discussion of the process of therapy is useful at this time as it pertains to memories of pivotal events that occurred for each of them.

Interventions and Mechanisms:

Encouragement and support. The therapist highlights each person's contribution to the changes in the relationship. The therapist encourages participants to continue to validate each other's feelings, desires, and wants.

Aftercare teaching. The therapist discusses a plan with all clients for relapse management and prevention. The plan should be in the context of how they can expect feelings of disconnection again at times, but what ways can they reconnect with one another.

End State:

All participants in therapy appear more flexible in their relationship positions to one another. Responses are empathetic and emotionally receptive. Both partners monitor and regulate negative affect in an emotionally engaged manner. A sense of connectedness exists between both partners, as well as a decrease in negative cycles.

Principal Investigator: [name]

Protocol Summary for IRB: Feasibility Study of Couple Therapy Treatment for Situational Couple Violence (IRB# 09-13-27)

Data Collection

For each couple, data will be collected at each visit. Data will be collected in two forms:

1. Self-report and partner-report questionnaires will be collected using several measures, all of which have adequate reliability and validity.
2. Physiological data will be collected by monitoring heart rate variability and cortisol level at the DCRU.

Screening Measures

In order to examine eligibility, demographics and some clinical data will be collected.

- CAGE questionnaire. CAGE is a brief alcoholism screening test (Mayfield D, McLeod G, Hall P.1974)
- Simple Screening Instrument for Substance (SSI-SA). Abuse (SSI-SA) The SSI-SA was intended as a brief screen of substance abuse symptoms. It was designed utilizing a binary (yes/no) response format to facilitate scoring and to minimize subjective interpretation of scores Center for Substance Abuse Treatment. (1994).
- Conflict Tactics Scale 2 (CTS2;Straus, Hamby, BoneyMcCoy, & Sugarman, 1996) assesses intimate partner violence based on partners' rating of their own and their spouse's conflict strategies, measuring the intensity and frequency of psychological/verbal and physical conflict. This scale has been shown to have good reliability and validity (Straus, Hamby, BoneyMcCoy, & Sugarman, 1996). This is also be used throughout the study to monitor couple's relationship change.
- Symptom Checklist (SCL90-R) (Derogatis, 1994) will be used to assess acute psychopathology. This measure will also be used throughout the study to monitor participants' mental health change.

Outcome Measures

Both behavioral and physiological measurements will be used to evaluate the effectiveness of conjoint therapy. No medical records will be reviewed at any time.

Physiological Measures: The change in emotion regulation of participants will be assessed by monitoring the HPA axis and PNS activity. The HPA axis is a major part of the endocrine system that controls reactions to stress. PNS is responsible for simulating the activities when the body is at rest. Therefore, monitoring the HPA axis and PNS activity together will enable assessment of emotion regulation (Porges, 2001). The HPA axis will be monitored using cortisol reactivity, which measures short term changes in the concentration of cortisol, a steroid hormone that is released in response to stress (Böhnke, Bertsch, Kruk, & Naumann, 2010). PNS activity will be monitored accessing vagal regulation (tone, reactivity); that is, the effects produced on the heart when only the parasympathetic nerve fibers are controlling the heart rate. Part of vagal regulation is heart rate variability monitoring, which will be done via eMotion HRV sensor (Please see attached information about the HRV sensor).

Couples will be separated upon arrival and will wait for 15 minutes to reach their resting period, in order for cortisol levels and heart rate to establish a more accurate baseline. The participants will relax by reading previously selected magazines or listening to calming music. They will be

Principal Investigator: [name]

Protocol Summary for IRB: Feasibility Study of Couple Therapy Treatment for Situational Couple Violence (IRB# 09-13-27)

measured for baseline levels of cortisol (via saliva samples) and heart rate variability (via eMotion HRV sensor). The participants will then wait for another 15 minutes.

Then, the couple will be reunited and cortisol and vagal reactivity of both partners will be measured following a discussion of a relationship conflict, in line with the Rapid Marital Interaction Coding System (RMICS) (Heyman & Vivian, 1993). Heart rate will be measured throughout this process. Saliva samples will be collected 15, 30, and 45 minutes following the task.

Mouth swipes will be used to measure saliva cortisol. Participants will be asked to place the oral swab into their mouth (under tongue), keep in place for 1 minute, and put the oral swab into the collection kit tube. eMotion HRV will be used to measure heart rate variability. eMotion HRV Sensor is an internally powered heart rate variability measurement device. During measurement, the sensor will be connected to the patient via two electrodes. The electrodes will be placed approximately along the electrical axis of the heart. The negative electrode (yellow) will be placed in the right infraclavicular fossa (just below the right clavicle). The positive electrode (red) will be placed on the left side of the chest, below the pectoral muscle in the left anterior auxiliary line. The research personnel will start the measurement by pushing the sensor power button down for one second. The green indicator light will light up and start blinking synchronously with the heart rate. At the end of the measurement, the research personnel will push the power button continuously for five seconds to end the measurement. The sensor will power down and the green indicator light will turn off.

Finally, each partner will complete questionnaires composed of the measures described below. It is expected that the lab session will last two hours. Participants will also complete measures on variables that may influence cortisol, such as conflict, unusual events, caffeine consumption, or exercise patterns (Kudielka, & Kirschbaum, 2003). After they finish completing all of the questionnaires, the therapist will instruct them in relaxation techniques and interventions to help deal with any negative emotions before they leave the assessment session.

The same procedure will be followed for each assessment phase (pre-test, post-test, and follow-up) and will take place during the hours of 4 pm to 8 pm because that is when the body's Circadian rhythm causes cortisol levels to normalize.

CTSC Dahms clinical unit will process and analyze the cortisol levels. The PI is in contact with [name], [name], and [name] for utilizing the Dahms Clinical Unit. For interpretation of the data, the PI is receiving consultation from [name] from Kent State University Department of Psychology. Please see the attached letter of commitment from [name].

Behavioral Measures: At each visit, participants will complete questionnaires measuring attachment patterns, affect regulation, dyadic adjustment, emotional abuse, and IPV. Both partners will fill out the questionnaires separately, in different rooms. The participants will fill out the questionnaires after the collection of physiological data.

Principal Investigator: [name]

Protocol Summary for IRB: Feasibility Study of Couple Therapy Treatment for Situational Couple Violence (IRB# 09-13-27)

Questionnaires include various measures about intimate relationships, all of which have been widely used in previous studies. These measures were chosen based on their conceptual and psychometric qualities. Statistical procedures (e.g., confirmatory factor analyses) will aid aggregation of these measures and the precise definition of latent variables. The measures that will be used are the following:

- Emotional Abuse Questionnaire (EAQ) (Babcock, Jacobson, Gottman, & Yerington, 2000; Jacobson & Gottman, 1998).
- Relationship Satisfaction Scale (Burns, & Sayers, 1992).
- Personal Assessment of Intimacy in Relationships (PAIR) (Schaefer, & Olson, 1981).
- Dyadic Adjustment Scale (DAS) (Spanier, 1976).
- Revised Dyadic Adjustment Scale (RDAS) (Busby, et. al 1995).
- Conflicts & Problem Solving Scale (CPS) (Kerig, 1996).
- Managing Affect and Differences Scale (MADS) (Arellano & Markman, 1995).
- Difficulties in Emotional Regulation Scale (DERS) (Gratz, & Roemer, 2004) will be used to assess affect regulation.
- Experiences in Close Relationships Scale (ECR) (Brennan, Clark, & Shaver, 1998) will be used to assess the attachment in relationships.
- Coping Inventory for Stressful Situations (CISS) (Endler & Parker, 1990) will be used to assess affect regulation.
- Family Daily Hassles Index (FDHI) (Rollins, Garrison, & Pierce, 2002) will be used to measure family stress/hassles and health status.
- Interpersonal Reactivity Index (Davis, 1983) will be used to measure empathy and perspective taking.
- Perceived Stress Scale (PSS10) (Cohen, et al 1983).

Participants can quit the study anytime they would like and there will be no penalty for dropping out of the study. If a participant drops out of the study, the PI will make at least 3 attempts to contact the participant, consisting of phone calls and a certified letter. The participants will be encouraged to perform a final follow-up visit.

Digital Data Collection of Patient Assessments: At the beginning of the study, the data management team (DMSAU) will obtain an email address for each research participant enrolled into the study. Throughout the study, this email address will be used to send a link to access the participants-rated survey. This email address will allow the participants to access the participants-rated survey from within the REDCAP server. Through this email address, the participants will be emailed a link to access self-report study assessments. This link will be created through the REDCap “management participant list” tool. This link does not carry any PHI or de-identified data. This link does not expose any information about the participants’ identity or other information. All participants’ responses will be recorded in a secured environment within the REDCAP server. As an additional security measure, the link will expire after the participants completes the participants-rated survey.

If any technical problems emerge that prevent the digital collection of data (accessing the REDCAP server, connectivity, computer technical issue, etc.), the participants can still complete

[figure not shown]
Principal Investigator: [name]

Protocol Summary for IRB: Feasibility Study of Couple Therapy Treatment for Situational Couple Violence (IRB# 09-13-27)

the paper version of the participant-rated survey. While participants will be encouraged to enter their responses digitally, they will continue to have the option of responding on paper if they so choose.

Participants will receive via email a 128-bit hash value (e.g. 3425eee5999025d4847fd3ca1b2a362c) that will uniquely identify them as the appropriate subject, essentially serving as a username and password in one. Participants will click on the link to go to the Self Report Survey in RedCap. All transmissions between the client and RedCap will take place over a 128 encrypted line. Answers will be stored in a MySQL database that is housed in the same HIPAA class data center as the above mentioned Oracle server. The Self Report Survey can still be completed on paper if that is the participant's preference or there are technological difficulties. In that instance, the data will be entered by study staff and will be double checked by second study staff.

Fig 1. Project Flow Chart

Principal Investigator: [name]

Protocol Summary for IRB: Feasibility Study of Couple Therapy Treatment for Situational Couple Violence (IRB# 09-13-27)

